video platform, e.g. Zoom. Online studies will provide assurances that we will not collect personal information or use the information for anything other than our scientific purposes. The initial information will disclose the use of 'cookies' to determine if the participant has performed the task before. Potential participants will have unlimited time to decide and will not be able to continue using the web site without their consent. To begin the experiment, participants will need to check boxes stating that they read through the consent sheet and agree to participate. Completion of this online form will be taken as consent to participate.

VI. BIOSTATISTICAL ANALYSIS

Error rates and response times (RTs) are the primary measures in these experiments. The nature of the stimuli, the number of items presented (the "set size") and the frequency of target presence (the "target prevalence") are varied across trials and blocks, respectively. Typically, trials are discarded if the RT is less than 200 ms and greater than 10000 ms. Interactions of interest include RT and prevalence, error rate and prevalence, target presence/absence and error rate, set size and error rate, set size and RT, and target type and error rate. All data are usually analyzed for statistical significance using analysis of variance (ANOVA) methods. We also use d' and criterion, the signal detection measures of detectability and bias to analyze performance. In experiments using the eyetracker, we are usually interested in number of fixations, fixation duration, and scan path.

VII. RISKS AND DISCOMFORTS

The only stresses and aggravations of these experiments are psychological. Some subjects find the tasks boring, while others find them challenging. Experts may have a particular, competitive desire to get the "right" answer. Occasionally, the sustained attention required can cause some subjects to have headaches or feel sleepy. Subjects are free to pause at any time, and may withdraw from the experiments if they wish.

In some of the experiments we will measure eye movements. There are no known risks associated with the eye movement system (pupil centre to corneal reflection system) to be used in these experiments. Illumination of the eye in these systems is less than 1 milliwatt per cm squared of near infrared light. Federal safety standards indicate that levels of 10 milliwatts per cm squared are not hazardous to adults or children.

VIII. POTENTIAL BENEFITS

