each of these effects, we derive measures of d' and criterion for each of the 16 pairs (combinations of one of four 'first blocks' with one of four 'second blocks'). We then subtract a baseline derived from all blocks of the second block condition. We use the second blocks as the baseline because we are looking for a change in the second block. In fact, it doesn't make much difference. Many second blocks in one pair are the first blocks in a subsequent pair and the baselines would be very nearly the same if all blocks were included as in Figure 2 above. Thus, for example, to assess the influence on criterion of Low Prevalence without Feedback (Condition 1 in the figures to follow) on High Prevalence without Feedback (Cond 3), we compute $\text{Criterion}(\text{pair 13}) - \text{Criterion}(\text{Cond 3})$. This is done for each of the 2080 pairs of blocks using the $d' > 0.5$ filter. The data for each of these 2080 "good" pairs of blocks are posted on the Open Science Framework at <https://osf.io/hck5n/>.

Figure 4 shows the change in D' as a function of pair with each dot representing one pair of blocks. Statistical tests are simple T-tests against a null hypothesis of no change in d' from block 1 to block 2. Three pairs, forming no obvious pattern, reach statistical significance (all $p = \sim 0.02$, all Cohen's $d = \sim 0.2$). As these are not corrected for multiple comparisons, these should not be considered strong effects. The general picture is of little or no effect of the first block of trials on d' in the second block of trials.

[figure not shown]

Figure 4: Change in d' on block 2 as a function of the nature of block 1. X-axis gives numerical values for each member of a pair where 1 = low prevalence, no feedback, 2 = low prevalence, with feedback, 3 = high prevalence, no feedback, and 4 = high prevalence, with feedback. P-values show results for simple t-tests, testing against the null hypothesis that there is no change in d' . Black lines show means +/- 95% confidence intervals.

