A different pattern is seen in the criterion data, plotted in Figure 5. Here, there are two clear clusters of significant effects. When block 1 has low prevalence and feedback, criterion on block 2 is more conservative (Pairs where Block 1 is low prevalence with feedback, all $p < 0.006$, Cohen's d between 0.2 and 0.5). When block 1 has high prevalence and feedback, criterion on block 2 is more liberal (Pairs where Block 1 is high prevalence with feedback, $p < 0.0005$, pair

44, $p = 0.017$; note that there are only 27 pairs of this variety in the dataset, All Cohen's d between 0.2 and 0.5). When block 1 does not have feedback, there is no effect on criterion in pair 2, except, perhaps, for 'high feedback' on Block 2 ($p < 0.028$, again, not corrected for multiple comparisons, Cohen's $d = 0.18$). This is the main finding of the paper. Criterion can be manipulated by the prevalence of the preceding block of trials, but only if the participants received feedback on that first block.

[figure not shown]

Figure 5: Change in criterion on block 2 as a function of the nature of block 1. P-values
show results for simple t-tests, testing against the null hypothesis that there is no change in
criterion. Black lines show means +/- 95% confidence intervals.

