Looking separately at changes in P(True Positive) and P(False Positive) responses, we see essentially the same pattern of results. For changes in True Positive proportions, pairs where Block 1 is low prevalence with feedback are significant (all $p < 0.005$) except when Block 2 is High Feedback ($p = 0.38$). Pairs where Block 1 is high prevalence with feedback are significant (all $p < 0.005$ except when Block 2 is Low Feedback which $p = 0.02$). The Low Feedback – High Feedback pair is not significant. For changes in False Positive proportions, pairs where Block 1 is low prevalence with feedback are significant (all $p < 0.05$). When Block 1 is high prevalence with feedback, results are significant when Block 2 is Low No Feedback, High No Feedback, and Low Feedback ($p < 0.01$). When Block 2 is High Feedback, there is no significant change ($p = 0.29$). The Low No Feedback – High Feedback pair is significant ($p = 0.001$). No other changes in P(True Positive) and P(False Positive) responses are significant. As noted above, removing the $d' > 0.5$ filter does not change the pattern of results. Limiting analysis to only the first pair of blocks for each participant preserves the direction of effects but some effects become statistically unreliable because of the loss of power.

Do the effects of one block on the next change with time between blocks?

Figure 5 shows that a block with feedback has an influence on the criterion in the next block. Is that effect transitory or persistent? The time between blocks is quite variable because participants could perform the second block immediately or from one to several days later. Accordingly, for each of the 16 pairs of blocks, we examined change in criterion as a function of time between blocks. The results are shown for four different time ranges in Figure 6.

[figure not shown]

Figure 6: Change in criterion as a function of time between the start of block 1 and start of block 2. 1440 minutes = 1 day. Colored lines are best-fit linear regressions for each of 16 pairs of block types. A) All data, B) Delay < 1 day, C) Delay < 2 hours, D) Delay < 15 min. Repeat pairs (e.g. Low Feedback -> Low Feedback) do not occur for shorter delays (C & D).

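### The 16 block-pair t-tests per outcome are uncorrected and the caveat is applied unevenly, so pair 44, one true-positive cell and the feedback-only claim need qualifying

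*Combined protocol and SAP*

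**What the plan says.** In the Specific Protocol, the section *How does one block influence the next?* names carry-over as the study's key question. The plan is to "derive measures of d' and criterion for each of the 16 pairs". For d', "Statistical tests are simple T-tests against a null hypothesis of no change in d' from block 1 to block 2". The caption of Figure 5 describes the same kind of test for criterion, "testing against the null hypothesis that there is no change in" criterion. Changes in true-positive and false-positive proportions are then reported over the same pairs. No alpha, sidedness, family of tests or adjustment is stated for any of these. Section VI (Biostatistical Analysis) of the general protocol says only that "All data are usually analyzed for statistical significance using analysis of variance (ANOVA) methods" and gives no multiplicity rule.

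Under *Statistical Analysis / Results*, Šídák's test is named after the d' ANOVA and after the response-time ANOVA. After the criterion ANOVA only pairwise comparisons are mentioned, with no method.

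The block-pair results are handled as follows:

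- **d'.** Three pairs at p of about 0.02, with no visible pattern: "As these are not corrected for multiple comparisons, these should not be considered strong effects".
- **Criterion, first block without feedback, second block High Feedback.** p < 0.028, offered as a possible exception and marked "again, not corrected for multiple comparisons".
- **Criterion, pair 44 (High Feedback to High Feedback).** p = 0.017, placed within the significant clusters. The only remark is that there are 27 such pairs.
- **True positives, High Feedback to Low Feedback.** p = 0.02, counted as significant with no caveat.
- **False positives, Low No Feedback to High Feedback.** p = 0.001, reported as significant.

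The conclusion reads "This is the main finding of the paper. Criterion can be manipulated by the prevalence of the preceding block of trials", with the proviso that this happens only when the first block had feedback.

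**The concern.** The multiplicity caveat depends on which cell is being discussed. A p-value of about 0.02 is set aside for d' and p < 0.028 is set aside for a no-feedback criterion cell. A p-value of 0.017 for criterion and one of 0.02 for true positives are kept. The lack of correction applies equally to all of them. The less central comparisons of conditions, for d' and response time, do receive a formal adjustment.

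Two things are at stake. The first is which individual cells may be called significant. The second is the negative half of the main finding, that a first block without feedback leaves the second unaffected. That half depends on discounting the one criterion exception, and on how the corresponding false-positive result is read.

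**Working it through.** **Inputs.** There are 16 tests per outcome (four first-block by four second-block conditions). Pair counts come from Table 5: 27 for pair 44, 147 for Low No Feedback to High Feedback, 118 for High No Feedback to High Feedback. The p-values are as listed in the text. Alpha = 0.05 and two-sided tests are assumptions, since neither is stated.

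**1. Reproducing the reported figures.** For a one-sample t-test, t = d√n with n − 1 degrees of freedom.

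- Pair 44: n = 27 and p = 0.017 imply d = 0.491, inside the stated range of 0.2 to 0.5 (d = 0.49 gives p = 0.0172). It reproduces.
- Discounted criterion cell, d = 0.18: with n = 147, p = 0.031, and over the rounding range d = 0.175 to 0.185 p runs from 0.036 to 0.026, which covers 0.028. With n = 118 the same range gives 0.060 to 0.047. The cell is therefore most likely Low No Feedback to High Feedback.

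**2. Threshold.** Šídák for 16 tests: 1 − 0.95^(1/16) = 0.0032. Bonferroni is almost the same: 0.05/16 = 0.0031. If the 16 tests were independent, the chance of at least one false positive would be 1 − 0.95^16 = 56%. The tests share participants and baselines, so that figure is only indicative.

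**3. Adjusted values**, 1 − (1 − p)^16, with bounds entered at the bound:

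| Outcome and cell(s) | Reported p | Šídák-adjusted | Below 0.05? |
|---|---|---|---|
| Criterion, High Feedback first (3 cells) | < 0.0005 | < 0.008 | Yes |
| Criterion, Low Feedback first (4 cells) | < 0.006 | up to 0.092 | Exact p needed |
| Criterion, pair 44 | 0.017 | 0.24 | No |
| Criterion, no-feedback first to High Feedback | < 0.028 | 0.365 at the bound | No, at the bound |
| d' (3 cells) | about 0.02 | about 0.28 | No |
| True positives, High to Low Feedback | 0.02 | 0.28 | No |
| True positives, other supporting cells | < 0.005 | up to 0.077 | Exact p needed |
| False positives, High Feedback first (3 cells) | < 0.01 | up to 0.149 | Exact p needed |
| False positives, Low Feedback first (4 cells) | < 0.05 | up to 0.560 | Exact p needed |
| False positives, Low No Feedback to High Feedback | 0.001 | 0.016 | Yes |

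The last row matters most for the negative half of the claim. It is a first block without feedback, it is the same pair as the discounted criterion cell in step 1, and it survives.

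**4. Would another standard rule give the current sorting?** Under Benjamini-Hochberg, ranking the criterion cells at their bounds, pair 44 is eighth (0.017 × 16/8 = 0.034) and the no-feedback cell is ninth (0.028 × 16/9 = 0.0498). Both pass, the second barely. The d' cells do not (0.02 × 16/3 = 0.107, with the unreported cells set to 0.5). Benjamini-Yekutieli drops pair 44 (0.115) and the no-feedback cell (0.168) and keeps the other seven criterion cells. None of the three rules keeps pair 44 while discarding the no-feedback cell, as the text does.

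**5. Do the two directions hold?** If no cell in a cluster has an effect, the largest p-value in that cluster is a valid, conservative p-value for the cluster, whatever the dependence between cells. After Low Feedback it is below 0.006; after High Feedback it is 0.017. Both are below the two-test Šídák level, 1 − 0.95^(1/2) = 0.0253. If all four first-block conditions form the family, the level is 1 − 0.95^(1/4) = 0.0127. Low Feedback still passes on its largest p, and High Feedback passes by Bonferroni on its smallest (4 × 0.0005 = 0.002).

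**The case against.** The strongest reply is that the main finding is a statement about the type of first block, supported by two coherent clusters, and that the cell p-values are detail. Step 5 bears this out for direction. Seven of the eight supporting criterion cells are at p < 0.006 or p < 0.0005, which is not comparable with the d' results. The text also weighs coherence: the d' cells are discounted partly because they form no pattern, and the two isolated delay correlations (p = 0.015 and 0.045) partly because they run the wrong way. It discloses awkward results too, namely the p = 0.001 false-positive change, the expected cells that fail (p = 0.38 and 0.29), the small count behind pair 44, and its non-significance in both halves of the second block. All of this stands and limits the consequence.

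It does not supply a rule. Coherence may justify a pooled test, but it does not make an individual cell at 0.017 significant while a neighbouring outcome at 0.02 is not. Nor does it explain why a surviving false-positive result leaves the feedback-only claim unqualified.

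Some stronger readings are tempting but unsupported:

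- *That criterion results were treated leniently throughout.* The caveat is attached to a criterion cell as well as to d'. The unevenness concerns one of eight supporting criterion cells, plus the true-positive cell.
- *That the error rate of the main conclusion is unknown, or the conclusion overturned.* The reported bounds already support both directions.
- *That the four outcomes amount to 64 independent tests.* d' and criterion are computed from the same true- and false-positive proportions, so a false-positive probability built on 64 independent tests is not meaningful.
- *That every ANOVA used Šídák.* It is named only for d' and response time.

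**Conclusion.** The concern holds in limited form. The tests of the key question are unadjusted, no alpha or family is declared, and results of similar strength are sorted differently. Under 16-test Šídák, pair 44, the no-feedback criterion cell and the High Feedback to Low Feedback true-positive cell all fail. Three High-Feedback criterion cells are secure, and the four Low-Feedback criterion cells are undetermined, not shown to fail. The false-positive change from Low No Feedback to High Feedback survives and cuts against the feedback-only wording. The direction of both feedback effects is not overturned.

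This rests on alpha of 0.05, two-sided tests, a family of 16 per outcome, bounds entered at their worst case, and each cell's own p-value taken at face value.

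**What to change.** State alpha and define the family as the 16 cells of each outcome. Report exact and Šídák-adjusted p-values for all 16 cells of d', criterion, true positives and false positives, and restate which remain significant. Describe pair 44 and the true-positive cell at 0.02 with the same caveat as the d' cells, or drop them from the list of significant results. Qualify the statement that carry-over requires feedback in the first block, citing the Low No Feedback to High Feedback false-positive result. Name the comparison method used after the criterion ANOVA.

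Optionally, add two pooled contrasts on criterion change, after Low Feedback and after High Feedback, each at about 0.025. These test the main claim directly and do not lean on a 27-pair cell.

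The cost is a short re-analysis of the 2,080 pairs already held, plus edits to the text. The downside is that a few cells lose significance.

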The central question of the present study is how experience with one level of prevalence, with or without feedback, influences performance on subsequent trials where either prevalence and/or feedback conditions could have changed. In the great bulk of research on prevalence effects, high prevalence trials were followed by low prevalence trials or participants experienced only a single prevalence level. Typically, feedback is not independently manipulated (but see Grown & Kukucka, 2021; Lyu, et al., 2021; Papesh, Heisick, & Warner, 2018; Weatherford, Erickson, Thomas, Walker, & Schein, 2020). Moreover, in previous studies, the change due to a previous discrete block of trials was not assessed.

In the present study, prevalence can be high or low and feedback can be present or absent. This yields four conditions: Low prevalence with feedback, Low prevalence without feedback, High prevalence with feedback, and High prevalence without feedback. There are 16 possible pairings of two consecutive blocks. In this study, the stimuli are skin lesions: either nevi (skin 'moles'; singular, nevus) or melanoma (skin cancer). A large dataset of over 300,000 decisions was collected on-line by participants using a medical image labeling app ("DiagnosUs" <http://diagnosus.com/>). Participants had varying levels of expertise from complete novice to MD as will be described later. Thus, in addition to allowing us to assess the influence of one prevalence X feedback combination on another, these data provide new evidence about prevalence effects in expert populations (K K Evans, Birdwell, & [name], 2013; K. K. Evans, Tambouret, Wilbur, Evered, & [name], 2011; Evered, 2017; Mitroff, Ericson, & Sharpe, 2017;

Reed, Ryan, McEntee, Evanoff, & Brennan, 2011; Trueblood, et al., 2021; [name], Brunelli, Rubinstein, & Horowitz 2013).

To anticipate the broad outlines of the results, LPE and weak PICC effects are produced with these dermatology stimuli. As in other studies with expert populations, our experts show these effects, as do novices. In terms of the influence of one block of trials on the next block, we find that, in general, experience with a low prevalence block with feedback makes one more conservative in any subsequent block while the experience of high prevalence with feedback makes one more liberal. A block without feedback does not appear to have a significant impact on the next block.

Methods

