To analyze the effect of one block on the next block, we derived all the pairs of blocks in the dataset. For each of the blocks, we calculated the true positive and false positive proportions and used these to derive the standard signal detection measure of d' and criterion (Note that we are refraining from using the term “sensitivity” because it is used to refer to d' in the behavioral science community and to the true positive rate in the medical community.) For the primary analyses, pairs were removed from analysis if either member of the pair produced a d' of less than 0.5. The task was relatively difficult and we had little control over the motivation of participants in online study of this sort. The probability of achieving a $d' > 0.5$ by guessing through an 80 trial block is $\sim 0.6\%$. A cutoff of 0.4 would permit over 2% of blocks to be pure guessing. A $d' > 0.5$ cutoff left 2,080 pairs of blocks. The distribution of those pairs is shown in

Table 5:

		Block N				
		Low, No Feedback	Low, Feedback	High, No Feedback	High, Feedback	
Block N+1	Low, No	29	140	151	134	454
	Low, Feed	92	110	150	218	570
	High, No	261	117	51	117	546
	High, Feed	147	218	118	27	510
		529	585	470	496	2080

Table 5: Counts of the 16 different pairs of Block N and Block N+1.

As can be seen, there is a good, if uneven distribution of pairs. There are fewer pairs on the diagonal where the condition is the same in Blocks N and N+1. In order to run the same block, twice in a row, participants needed to encounter that condition last on Day K and first on Day K+1 since the same condition could not be run twice on the same day. The marginals show that this distribution of the four different conditions is very roughly uniform.

First, we compare performance in the four conditions, regardless of their position the sequence of sessions for each observer. Figure 2 shows the signal detection measures of d' and criterion, “c”. These values cannot be computed if $p(\text{True Positive}) = 1.0$ or $p(\text{False Positive}) = 0.0$. Accordingly, in keeping with one standard practice, we add $\frac{1}{2}$ of a False Positive error to each False Positive count (Hautus, Macmillan, & Creelman, 2021).

[figure not shown]

Figure 2: D' and Criterion as a function of condition. Each dot represents one of 2080 blocks of data. Black lines show mean and +/- 95% CI of the mean.

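### The claim that prevalence carries over only after feedback blocks rests on comparing significant with non-significant cells; the no-feedback contrast and the interaction are not reported

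*Combined protocol and SAP*

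**What the plan says.** All places are in the Specific Protocol.

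- *How does one block influence the next?* sorts consecutive blocks into 16 pairs. Conditions are coded 1 = low prevalence without feedback, 2 = low with feedback, 3 = high without, 4 = high with; pair 14 is condition 1 followed by condition 4. Each second block is scored as a change: "We then subtract a baseline derived from all blocks of the second block condition". The choice is defended on the ground that "the baselines would be very nearly the same if all blocks were included as in Figure 2 above".
- Each cell is tested by a simple t-test against no change. The Figure 5 caption adds: "Black lines show means +/- 95% confidence intervals".
- Criterion results: after low prevalence with feedback, all p < 0.006; after high prevalence with feedback, p < 0.0005, except pair 44 (p = 0.017, 27 pairs). For the rest: "When block 1 does not have feedback, there is no effect on criterion in pair 2, except, perhaps, for 'high feedback' on Block 2". That exception has an uncorrected p < 0.028 and d = 0.18.
- The conclusion, labelled the main finding: "Criterion can be manipulated by the prevalence of the preceding block of trials, but only if the participants received feedback on that first block".
- On false positives, the same section says: "The Low No Feedback – High Feedback pair is significant ($p = 0.001").
- The introduction is more cautious: "A block without feedback does not appear to have a significant impact on the next block".
- *Statistical Analysis / Results* comments on Table 5: "As can be seen, there is a good, if uneven distribution of pairs".

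**The concern.** The main finding makes two claims: preceding prevalence moves criterion after feedback blocks, and it does not after blocks without feedback. The first is tested. The second is read from cells that failed to reach significance. A significant cell beside a non-significant one does not test the difference between them, and non-significance does not show absence.

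Two estimates would settle it: the low-minus-high contrast after no-feedback blocks with its interval, and the difference between that contrast and the one after feedback blocks. The text gives neither. The ANOVA and Šídák comparisons earlier in the results compare conditions regardless of sequence, so they do not address carry-over.

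A secondary matter is the zero line. The baseline for each cell includes the cell itself and is weighted by how often each predecessor happened to occur. This affects single-cell tests, including the one no-feedback exception.

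**Working it through.** **Inputs.** Table 5 counts, by second block, in predecessor order 1, 2, 3, 4: condition 1: 29, 140, 151, 134 (454); condition 2: 92, 110, 150, 218 (570); condition 3: 261, 117, 51, 117 (546); condition 4: 147, 218, 118, 27 (510). The p-values and effect sizes are those reported for Figure 5. Assumptions: a plain pooled-mean baseline, equal SD across cells, independent pairs.

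**1. Reproducing the plan's figures.** With t = d√n, p = 0.028 needs d = 0.183 at n = 147 (pair 14) and 0.205 at n = 118 (pair 34). The stated d = 0.18 therefore fits pair 14, the pair also flagged for false positives. Pair 44 (p = 0.017, n = 27) gives |d| = 0.49, within the stated 0.2 to 0.5.

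**2. Feedback contrast (low minus high).** The smallest |d| compatible with each p-value is t/√n.

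| Second block | after 2 (p = 0.006) | after 4 (p = 0.0005; pair 44: 0.017) | sum |
|---|---|---|---|
| 1 | 0.236 | 0.308 | 0.544 |
| 2 | 0.267 | 0.239 | 0.507 |
| 3 | 0.259 | 0.331 | 0.590 |
| 4 | 0.188 | 0.491 | 0.679 |

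The mean is 0.58 SD, a floor because all but pair 44 come from upper bounds on p. The baseline cancels, since both cells in a row have the same value subtracted.

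**3. Precision of the unreported no-feedback contrast.** Per second-block condition, SE = √(1/n_low + 1/n_high) = 0.203, 0.132, 0.153, 0.124.
- Equal weights: SE = ¼√(sum of squares) = 0.078; half-width 1.96 × 0.078 = 0.153.
- Inverse-variance weights: SE = 0.073; half-width 0.142.
- As a share of 0.58 SD: 0.142/0.58 = 25% and 0.153/0.58 = 26%.

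The feedback contrast has an equal-weight SE of 0.074, so the difference of the two contrasts has SE √(0.078² + 0.074²) = 0.107.

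**4. Baseline.** A cell's share of its own baseline is its count over the row total: from 27/510 = 5% (pair 44) to 261/546 = 48% (pair 13). Its deviation equals (1 − share) times its difference from the other three predecessors.

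If carry-over is +D after condition 2, −D after condition 4 and zero otherwise, the baseline moves by (n₂ − n₄)/row total:
- second block 1: (140 − 134)/454 = +0.01D
- second block 2: (110 − 218)/570 = −0.19D
- second block 3: 0
- second block 4: (218 − 27)/510 = +0.37D

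Removing these shifts from the minimum d values gives D of about 0.22 to 0.36 SD. That alone puts about −0.08 to −0.13 SD into pairs 14 and 34.

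**5. Sign of the exception.** Deviations in a row sum to zero when weighted by n: 147·d14 + 218·d24 + 118·d34 + 27·d44 = 0, with d24 at least 0.188 and d44 = −0.491.
- If d14 = +0.18: d34 = −(26.5 + 41.0 − 13.3)/118 = −0.46, which would have been plainly significant and is not reported.
- If d14 = −0.18: d34 = −(−26.5 + 41.0 − 13.3)/118 = −0.01.

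So the exception is a liberal shift, the same direction as the tilt. Letting d24 rise to 0.28, where pair 34 would just miss significance (d34 = −0.18), the no-feedback contrast in this row runs from −0.17 to 0.00 SD (|z| at most 1.4).

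**The case against.** The best reply is that the conclusion is probably right in direction. If the no-feedback contrast were near zero, the difference would be about 0.58/0.107, or more than 5 standard errors. In the one second-block condition where the reported figures allow a reconstruction (high prevalence with feedback), the difference is about 0.77 to 0.85 SD, z about 3.2 to 3.6 before allowing for repeated pairs. The text also hedges: the exception is flagged as uncorrected, the introduction claims only no significant impact, cell intervals are plotted, and the data are posted. All of this stands. It supports a larger shift after feedback, not the absence of one without it.

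The one-quarter figure uses a floor. With d up to 0.5 per cell the feedback contrast could approach 1.0 SD and the fraction would fall to 14% to 15%. Repeated pairs per participant, with conditions assigned within participants, could make the contrast more or less precise than shown. The check on first pairs only removes the repeats and is said to preserve the direction of effects, but no no-feedback contrast is reported there either.

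Two stronger readings are tempting and should not be drawn:

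- A reader might take the false-positive result for pair 14 (p = 0.001) as proof of a prevalence effect without feedback. It is one cell against the tilted baseline, on a different outcome, and not a low-versus-high contrast.
- A reader might infer that the baseline produced the feedback versus no-feedback pattern. The mean own-cell share is similar on both sides (0.26 with feedback, 0.24 without), and the baseline cancels in the contrasts that matter.

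**Conclusion.** The concern holds for the word 'only'. The opposite shifts after low-prevalence and high-prevalence feedback blocks are secure, at an average contrast of at least about 0.58 SD. The claim of no carry-over without feedback lacks its deciding estimate. On Table 5, that estimate would have a half-width of about 0.14 to 0.15 SD, so even a zero value would leave up to about a quarter of the 0.58 SD floor open. This rests on equal SDs and independent pairs.

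The baseline is a secondary fault. It makes the pair 14 criterion exception uninterpretable as it stands: liberal, in the direction of the tilt, and possibly in part an artefact. The false-positive result for that pair deserves discussion but decides nothing. The documents do not show that the main finding is false, or that no-feedback blocks carry over.

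**What to change.** Fit one linear mixed model for second-block criterion, with Block N prevalence × Block N feedback × Block N+1 condition and a participant random effect. State the weighting over Block N+1 conditions and report with 95% intervals:

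1. the low-minus-high contrast after feedback blocks;
2. the same contrast after no-feedback blocks;
3. their difference.

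Item 3 shows whether carry-over depends on feedback; only the interval in item 2 bears on 'only'. Run the same model for the false-positive proportion and discuss the pair 14 result beside item 2. If Figures 4, 5 and 7 keep a baseline, leave the plotted pair out of it and carry its standard error into the intervals.

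Replace the 'only' clause with wording the intervals support, for example: the shift was larger after feedback blocks [difference, 95% CI]; after blocks without feedback it was [estimate, 95% CI]. Keep 'larger' only if item 3 supports it.

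Cost: re-analysis of data already collected and posted, some changed per-cell p-values, and possibly a softer headline.
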